Only one wound per subject will be included in the study. Subjects with multiple wounds will have each wound measured for volume. The wound with the largest volume meeting all eligibility requirements will be chosen for inclusion in the study. The etiology of the chosen wound, and if it is a new or recurring, will be documented.

Randomization and Blinding Procedure

Prior to study initiation, Active and Control samples will be prepared in sealed and labeled as A or B, also randomization envelopes will be provided to the research staff and used to obtain randomization assignment. Within each randomization envelope, there is an assignment of A or B. After run-in evaluation, the subjects wound will be debrided and dressed with SOC. At the end of the procedure, subjects who continue to meet all inclusion and no exclusion criteria will be randomized in a 1:1 ratio to be treated with either Control or Celliant therapies, stratified by wound size (greater than size of 4 cm²) and study center. Study staff will use the randomization number labels and sock assignment of socks A or B contained in the envelope. The number will become the subject ID. The research staff will note the randomization number and the treatment assignment letter (A or B) on the CRF. The key, indicating therapy assignments (Active or Control), will only be available to staff not directly involved in the study until after the subject has completed study activities.

Visit Schedule

Study procedures for each phase of study are outlined below. In a later section, details on each study procedure are described, including equipment designation.

Screening

- 1. Explain purpose and nature of the study and obtain signature on the informed consent document.
- 2. Screen the subject against protocol inclusion and exclusion criteria, including all pertinent tests.
 - a. ABI and/toe pressure
 - b. Ulcer History, measurement, and classification
 - c. Urine Pregnancy test (if indicated)

Baseline (may be done as same day as screening procedures)

- 1. Obtain general medical history and demographic information and social history
- 2. Complete a physical examination, body weight, height, and vital signs, including measurement of resting heart rate, respiratory rate, and blood pressure while seated.
- 3. Select the target ulcer
- 4. Obtain complete history pertinent to DFU disease including duration of the target ulcer,

previous and current treatment.

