7. Perform hyperspectral imaging assessment on the dorsal and plantar aspects of the foot.

10. Wounds will be dressed SOC and offloaded per physician discretion.

Week 2 Run-in/Therapy Initiation:

- 1. Assess target ulcer
- 2. Perform debridement if indicated. Debridement is to be performed using curette, scissors, scalpel, or forceps.
- 3. Perform standardized photography of the study wound.
- 4. Assess the post-debridement ulcer area (cm²), perimeter (cm), and greatest depth (cm) using the inSight device.
- 5. If wound size (ulcer area) increases/decreases by 30% or more, patient will be deemed a screen failure and removed from the study.
- 6. If wound size (ulcer area) increases/decreases by less than 30%, patient wound will enter the study and randomized to either the Celliant Active or Control treatment arm.
- 7. Perform hyperspectral imaging of the dorsal and plantar aspects of the foot
- 8. Perform pain assessment.
- 9. Collect all relevant concomitant medication
- 10. Wound will be dressed with SOC and either Celliant Active or Control Sock applied.
- 11. Wound will be offloaded.
- 12. Provide subject with any additional medical socks needed until the next visit. Instruct the subject to change the socks if they become wet, soiled, or bloody and under any conditions dictated by PI instructions.

Therapy/Treatment Phase

Study Visit 1-11:

- 1. Document study compliance information from the subject
 - a. Amount of time the sock was worn throughout the week
 - b. Was it worn during the day/night?
 - c. When/why the sock was changed.
 - d. Has the sock been on in the 3 hours leading up to the appointment?
- 2. Remove sock and dressing and immediately perform hyperspectral imaging of the dorsal and plantar aspects of the foot if wound is active or closed.
- 3. Assess target ulcer (if wound has closed, document as such, perform steps 7 and 8 and

- skip to Study Visit Wound Closed).
- 4. Debridement is to be performed, if indicated, using curette, scissors, scalpel, or forceps. If debridement is necessary at weekly visits, all therapy must be removed and replaced post-debridement.
- 5. Collect 4 tissue specimens at week 3 and at week 6. Two in RNA later and two in DNA/RNA shield.
- 6. Perform standardized photography of the study wound.
- 7. Assess the ulcer area (cm²), perimeter (cm), and greatest depth (cm) using the inSight device if the wound is deemed closed by the physician, skip to EOS visit.

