 - O IODOSORB Gel is a sterile antimicrobial dressing formulation of Cadexomer lodine. When applied to the wound, IODOSORB absorbs fluids, removing exudate, slough and debris and forming a gel over the wound surface. As the gel absorbs exudate, iodine is released, killing bacteria and changing color as the iodine is used up. https://www.smith-nephew.com/professional/products/advanced-wound-management/iodosorb-iodoflex/iodosorb-gel/
 - Hydrofera Blue READY Foam Dressing protects wounds against infection with broad-spectrum antibacterial properties and helps with healing and managing chronic, acute and traumatic wounds. This ready-to-use, noncytotoxic dressing assists with managing moisture, creating an ideal healing environment that does not draw out the process and helps control exudate. https://hydrofera.com
 - AQUACEL EXTRA Hydrofiber Dressing is composed of two layers of Hydrofiber technology stitched together. Specifically suited to help manage moderate to highly exuding wounds. https://www.convatec.com/products/pc-wound-leg-ulcers/aquacel-extra-hydrofiber-dressing
- Offloading: All subjects who can be offloaded will wear the DH OffLoading Walker. This
 is a removable offloading boot that reduces shear force by stabilizing the foot and ankle
 at 90°. https://www.ossur.com/injury-solutions/products/foot-and-ankle/walkers/dh-offloading-walker. If patients cannot be offloaded as defined above, a method of
 offloading will be used and documented, both type and reason why the Walker was not
 used.

Delegation of Responsibilities

Task		Responsibility				
		Nurse	CRC			
Determine eligibility of subjects	Х					
Obtain informed consent	Х	Х	Χ			
Randomization	Х	Х	Х			
Medical history	Х	Х	Χ			
Dressing removal	Х	Х	Χ			
Wound assessment of infection and closure	Х					
Tissue Collection	Х	Х	Χ			
Wound measurements	Х	Х	Χ			
Study withdrawal assessment	Х					
VPT	Х	Х	Χ			
10-gram monofilament test	Х	Х	Χ			
Hyperspectral imaging	X	X	X			
Skin perfusion pressure measurements	Х	X				
Transcutaneous Oxygen measurements	X	Χ	Χ			
Pain assessment	X	Х	Х			
Concomitant medications	Х	Х	Χ			
Subject compliance assessment and review	Х	Х	Х			
Administer patient reported outcomes	Х	Х	Х			
Dressing Application	Х					
Study Device Application	Х	Х	Χ			
Offloading	Х					
CRF completion/corrections	Х	Х	Χ			
CRF/eCRF signature	Х					
SAE/AE assessments	Х					
Update and maintain study documents	Х	Х	Х			
SAE reporting and data clarifications	X	X	Χ			

Schedule of Events Table

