Internal audits are done periodically to assure regulations, guidelines and protocols are adhered to appropriately. Patient binders are reviewed for proper informed consent process documentation, case report forms are compared to the source documents and reviewed for accuracy and an independent review of the inclusion and exclusion criteria using a checklist. Additionally, the use of an auditing and monitoring tool which includes sections on consent, HIPAA, on study/treatment, off treatment/off study and a general section. Weekly meetings occur to go over each study. If there are any issues that arise, they are brought up and discussed at the meeting.

4. Statistical Analyses

General Statistical Considerations

This study is a prospective, sham-controlled, subject and evaluator blinded, 1:1 randomized, multicenter clinical study. The duration of the study is up to four months for randomized subjects. Sample size may not be reduced less than the expected total enrollment of 254 evaluable subjects total but may increase up to a total of 2500 evaluable subjects. Sample size will increase based on actual attrition that is expected to be between 5 and 15%.

The purpose of this study is to evaluate safety and efficacy outcomes related to the Celliant Sock (CS). The p-value thresholds for determining statistical significance are 0.05 and 0.025 for 2- and 1-sided tests, respectively, unless otherwise specified.

Protocol #: HGX2020-01

Data will be presented using summary statistics. For example, continuous data may be displayed with the mean, median, minimum, maximum, and/or standard deviation, while categorical data may be displayed as proportions and counts.

Any changes to the analysis of the trial data will be documented either in a future protocol amendment or in the SAP.

Randomization

Randomization will be conducted in a 1:1 ratio of the Treatment Group (Celliant Sock, n=127) or to a sham Control Group (placebo sock, n=127). Randomization will be performed within randomly selected block sizes of 3 and 6 with equal probability of group assignment stratified by study center and wound size (greater than size of 4 cm²).

A Sponsor-designated independent statistical consultant will provide the randomization list. Sponsor personnel directly involved in the management, conduct, and reporting of the study will not have access to randomization assignments until the study is completed.

Analysis Population

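### Masking rests on two trial-wide letters that site staff read and record: group membership is open, learning one letter's meaning unmasks every subject, and the next letter can be guessed above chance

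*Combined protocol and SAP*

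**What the plan says.** In section 3, Randomization and Blinding Procedure, the supply has two codes for the whole trial: "Prior to study initiation, Active and Control samples will be prepared in sealed and labeled as A or B". The envelope carries the same code: "Within each randomization envelope, there is an assignment of A or B". Staff take sock A or B accordingly, and "The research staff will note the randomization number and the treatment assignment letter (A or B) on the CRF". The key that links letters to Active and Control is withheld from study staff "until after the subject has completed study activities". Section 4, Randomization, says that sponsor personnel "will not have access to randomization assignments until the study is completed".

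That same subsection prints the scheme: "Randomization will be performed within randomly selected block sizes of 3 and 6 with equal probability of group assignment stratified by study center and wound". The last of these factors is wound area, cut at 4 cm².

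At treatment visits the instruction to site staff is: "Remove sock and dressing and immediately perform hyperspectral imaging of the dorsal and plantar aspects of the foot". The Delegation of Responsibilities table ticks Nurse, CRC and the first role column for randomization, device application, hyperspectral imaging, wound measurement, pain assessment and CRF completion. The row "Wound assessment of infection and closure" is ticked in the first column only, and that column is also ticked for randomization and device application.

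The safeguards given are a visually identical control sock (Device Description) and the restricted key. Section 4, General Statistical Considerations, describes subjects and evaluators as blinded.

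**The concern.** A restricted key hides what a letter means. It does not hide which subjects share a letter, and the people who enrol and assess can know that for every subject. Three routes follow.

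- **Inference.** Outcomes can be compared by letter, and if the sock works the comparison points to the active letter.
- **Disclosure.** If the meaning of a letter becomes known for one subject, it is known for all. The key wording in section 3 ties release to the individual subject's completion, which makes this a practical risk while others are still on study.
- **Prediction.** Earlier letters in a stratum and the block sizes are visible, so the next letter is partly predictable before the envelope is opened. Eligibility at therapy initiation turns on a 30% change in area measured after debridement, debridement is at the physician's discretion, and the measuring roles are the ones that randomize.

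The outcomes at stake are complete closure, a physician judgement that is the key secondary endpoint, and VAS pain, which the subject marks but staff administer and which is third in the testing hierarchy. The Interim Analysis section sets up a communication firewall so that subjects before and after the interim are handled alike. A letter that can be decoded works against that aim.

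**Working it through.** **1. Inputs.** Difference 8.2 and SD 21.7 in percent change in StO2 at week 12, two-sided 0.05, power 0.85, 254 evaluable (Sample Size Justification). Blocks of 3 and 6, strata of center and wound size (section 4, Randomization). Two sites and two size classes give 4 strata, or about 254/4 ≈ 64 subjects each.

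**2. The plan's own figure.** Normal approximation: 2 × (1.960 + 1.036)² × (21.7/8.2)² ≈ 125.8, so 126 per arm (252). The noncentral t gives 127 per arm, total 254, power 0.851. The stated size reproduces, so the effect and SD can be used as the plan's own.

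**3. Which letter is active.** With m subjects per letter and one week-12 value each, the probability that the higher-mean letter is the active one is Φ(8.2 / (21.7 × √(2/m))).

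| m per letter | Probability |
|---|---|
| 5 | 0.72 |
| 10 | 0.80 |
| 20 | 0.88 |
| 30 | 0.93 |
| 60 | 0.98 |
| 127 | 0.999 |

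One site's half of 254, if sites are equal, is about 63 per letter (0.98). With no true effect every entry is 0.50.

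**4. After the primary analysis.** Closure is tested, and the trial continued for it, only if the primary endpoint succeeds at 254. Suppose two equal sites and a simple comparison of means, with overall z = (z₁ + z₂)/√2. Given z, z₁ is normal with mean z/√2 and variance 1/2, so P(z₁ > 0) = Φ(z). At the success threshold z = 1.96 this is 0.975. Given success, a site's own tally points to the active letter with at least that probability, whatever the true effect.

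**5. The next letter.** A block of 3 cannot be 1:1, so I assume 2:1 or 1:2 with equal chance.
- Block of 6, best guesser: 3 + 32/20 − 0.5 = 4.1 correct of 6 (68.3%).
- Block of 3, best guesser: 1/2 + 2/3 + 2/3 = 1.83 correct of 3 (61.1%).
- Equal mix: (4.1 + 1.83)/9 = 65.9%. A simulated best guesser who does not know the current block size reaches 65.6% (4,000 runs of 64 subjects).
- Plain tally, guessing the letter used less so far: 59% within stratum, 56% if wound size is ignored.
- Only about 3% of assignments are certain under the mix.

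**6. The next treatment.** This needs both steps. At 20 per letter: 0.884 × 0.659 + 0.116 × 0.341 ≈ 0.62.

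**7. With subject-specific kit numbers.** Earlier assignments are not visible, so the guess rate is 50% for any block size, and StO2 cannot be pooled by code.

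**The case against.** The documents do not show that sites hold the information in usable form. They say who takes the images, not who extracts StO2 or whether staff see change from baseline. That is fair, and step 3 is conditional on it; but no section masks the values or sends them to a central reader.

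A probability of 0.88 at 20 per letter is not proof: the same inputs would give a significant difference between letters only about 22% of the time. It also needs 40 subjects with week-12 data. Both points stand. The 66% is a ceiling for someone who filters optimally within stratum. That stands too, and the plain-tally figure is the more realistic one.

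The delegation table shows who may do a task, not that one person does all of them. True, but nothing separates the roles. StO2 is a camera reading, and the 30% rule uses device-measured area, so those are less open to judgement. I accept this, apart from the discretion over debridement before the area is measured.

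Enrolment past 254 may at first reflect replacement for attrition, so the signal in step 4 is clear only once enrolment runs on after the primary analysis.

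**Conclusion.** The point holds as an avoidable weakness in the masking. Group membership is open by design, and the code is inferable with probability about 0.80 to 0.98 between 10 and 60 subjects per letter, if staff see StO2 and the planned effect is real. If the trial continues past a successful primary analysis, it is inferable largely whatever the true effect. The next letter is guessable at 59% to 66% against 50%, given the assumed filling of blocks of 3. This is opportunity for bias, chiefly in closure and VAS pain; it is not evidence that bias will occur.

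A reader might infer more, which the text does not support:
- That each sock is marked, or that the letter is written beside weekly StO2. The text says samples are labelled and the letter is noted on the CRF with the randomization number.
- That a letter is handed out at every visit. Sock Use Instructions gives 10 pairs at the start and more as needed.
- That the treatment itself is guessable two times in three. That ceiling is for the letter.
- That thousands of subjects would be affected. 2500 is a maximum; 508 is the preplanned total, with efficacy and futility stops before it.
- That any bias would be invisible. Selective enrolment could show in baseline or screen-failure imbalance. The end-of-study question on perceived arm is put to subjects, however, not to assessors.

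**What to change.** In section 3, Randomization and Blinding Procedure, replace the A and B labels with subject-specific kit numbers from the independent statistician's list, for both the initial supply and resupply. The envelope gives a kit number, the CRF records only that number, and no two subjects share a code. If subjects are already enrolled under letters, use kits for all new randomizations and all resupply; letters already seen cannot be undone.

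As a secondary safeguard, move the block sizes from section 4, Randomization, to the statistician's restricted file. Reconcile the two statements on when assignments may be known: one refers to the subject's completion, the other to the study's. With kits, an early disclosure would unmask one subject instead of all.

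The cost is relabelling, a short amendment and more inventory work, because socks can no longer be drawn from bulk A or B stock. No extra patients, staff or procedures are needed.

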- Presence of osteomyelitis that requires treatment outside the study scope.
- Need for wound management outside the study scope

Celliant Clinical Trial Protocol
PI: [name]
Protocol #: HGX2020-01

 Or for any reason that may, in the opinion of the Investigator, affect negatively the wellbeing of the subject.

If for any reason the subject is withdrawn from the clinical investigation, the Investigator will inform the subject accordingly.

3. Clinical Investigation Plan

Description of Trial Design

This study is designed as a prospective, multi-center, double-blind, 1:1 randomized clinical trial to assess the clinical safety and efficacy of Celliant® Diabetic Medical Socks to increase tissue oxygenation and complete wound closure.

Investigational Sites

University of Texas Southwestern, Department of Plastic Surgery

PI: [name], DPM, MPH

Location: Dallas, TX

Parkland Hospital, Department of Plastic Surgery

PI: [name], DPM Location: Dallas, TX

Duration of Subject Participation

- Screening: Within 7 days Run-In initiation
- Run in Evaluation: 2 weeks of evaluation
- Treatment period: Up to 12 weeks
- Follow-up period: Up to 3 months post wound closure event
- Total duration of subject participation: Up to 28 weeks

Screening and Enrollment

Patients who present to the investigator's institution (through clinic admission, direct transfer from another facility, or through the emergency room) may be recruited to participate in the study. No direct marketing for subject recruitment will be done.

Patients approached for study participation will be at least 22 years of age at the time of consent, will undergo wound assessment, and meet all eligibility requirements. Those meeting eligibility criteria for the study will have the study explained to them by the Investigator. An Informed Consent Form will be provided to sign according to Section 11 prior to undergoing any study procedures. Patients will be encouraged to ask questions of the investigators. It will be made clear to the patient that not participating in the study will in no way influence the treatment plan or the relationship with the physician.

Celliant Clinical Trial Protocol
Protocol #: HGX2020-01

Wound Selection

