- 8. Perform SPP and tcPO2 measurements at Visit 4 (maybe be taken instead at visit 5 or 6 if subject has not been wearing their treatment sock leading up to the visit or misses this visit).
- 9. Collect all relevant concomitant medication
- 10. Perform pain assessment.
- 11. Redress the wound with standard of care (if wound is still active) and apply Celliant Active or Control Sock and apply offloading (if indicated).
- 12. Wound will be offloaded.
- 13. Provide subject with any additional medical socks needed until the next visit. Instruct the subject to change the socks if they become wet, soiled, or bloody and under any conditions dictated by PI instructions. Instruct the subject that they must wear the sock at all times and that including the 3 hours leading up to the next study visit.

Study Visit - Wound Closed

- 1. The study wound is defined as closed when there is complete skin re-epithelialization without drainage or dressing requirements confirmed by the evaluating physician at 2 consecutive study visits 2 weeks apart.
- 2. At this visit the subject will perform the EOS evaluation and enter the follow-up phase of the study.

Study Visit 12/EOS

- 1. If the study wound closes prior to the 12-week study mark, subjects will perform EOS visit at the time of wound closure. See Study Visit Wound Closed.
- 2. A subject whose wound does not close completely by week 12 will exited from the study after the week 12 wound evaluation.
- 3. Document study compliance information from the subject
 - a. Amount of time the sock was worn throughout the week
 - b. Was it worn during the day/night?
 - c. When/why the sock was changed.

- d. Has the sock been on in the 3 hours leading up to the appointment?
- 4. Remove sock and dressing and immediately perform hyperspectral imaging of the dorsal and plantar aspects of the foot if wound is active or closed.
- 5. Assess target ulcer (if wound has closed, document as such, perform steps 7-12 and skip to Study Visit Wound Closed).
- 6. If the subject still has a large enough wound, collect 4 tissue samples. Two in RNA later and two in DNA/RNA shield.
- 7. Perform standardized photography of the study wound.
- 8. Assess the ulcer area (cm²), perimeter (cm), and greatest depth (cm) using the inSight device.
- 9. Perform SPP if wound is active or closed.
- 10. Perform tcpO2 if wound is active or closed.
- 11. Perform pain assessment
- 12. Ask the subject if they thought they were in the active or control group

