The VAS is the most commonly used scale for assessing pain [60]. The VAS is a simple scale that consists of a 10cm line anchored at one end by a label that indicates total absence of the measure being evaluated and at the other end by a label that indicates the worse imaginable presence of the measure being evaluated. The subject marks on the line the spot for the intensity of the measure, which is then measured using a ruler (in mm units).

Infection Evaluation

The following clinical indicators of significant bacterial infection will be recorded as present or absent for the study wound. 'Significant Bacterial Infection Clinical Indicators' are defined in this study as those presenting as excessive beyond which would typically be expected given the clinical condition and nature of the wound type.

- local heat
- spreading redness
- swelling
- increased purulent exudate (draining pus)
- odor
- cellulitis
- loss of function
- fevers
- chills

Sock Use Instructions

The subjects will be provided with 10 pairs of socks on the initial visit and instructed that the socks may be washed as normal laundry as needed (bleach or no bleach). Subjects will be supplied additional pairs as needed on a case by case basis. The sock change frequency will be dictated by the physician; however, the subject will be instructed to change the sock as with any other sock if it becomes wet, soiled, or bloody.

Patient Reported Outcomes

The Diabetic Foot Ulcer Scale – Short Form (DFS-SF) (Appendix B) will be used to collect patient reported outcomes in this trial. The DFS questionnaire is designed to assess the impact of foot ulcers and their treatment on quality of life in people with diabetes.

Excluded Medications/Treatments

During the study procedures, the study subjects will refrain from using hyperbaric oxygen therapy (HBOT) and any cellular or tissue-based products (RegranX etc).

Standard of Care

- All study wounds will be debrided per physician discretion and documented.
- Wound Dressing: Two wound care treatments will be available, depending on wound status and physician discretion

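### The only rule on access to the A/B key that reaches site staff expires when one subject completes, which does not fit the blinding promised elsewhere

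*Combined protocol and SAP*

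**What the plan says.** Protocol section 3, Randomization and Blinding Procedure, sets up the coding. "Active and Control samples will be prepared in sealed and labeled as A or B", and each envelope holds one of those two letters. "The research staff will note the randomization number and the treatment assignment letter (A or B) on the CRF". The key that translates the letters into Active or Control "will only be available to staff not directly involved in the study until after the subject has completed study activities".

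Other sections state what blinding is meant to achieve:

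- Section 3, Description of Trial Design, calls this a "prospective, multi-center, double-blind, 1:1 randomized clinical trial".
- Section 4, General Statistical Considerations, calls it "sham-controlled, subject and evaluator blinded, 1:1 randomized".
- Section 4, Randomization, keeps assignments from involved Sponsor personnel for the whole length of the study. It does not mention site staff.
- Section 4, Interim Analysis for the Key Secondary Endpoint, keeps wound closure blinded to everyone but the Interim Analysis Committee up to the final closure analysis. It also asks for a firewall so that handling of subjects does not change after the interim.

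On the endpoint itself, Study Visit - Wound Closed requires closure to be "confirmed by the evaluating physician at 2 consecutive study visits 2 weeks apart".

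**The concern.** The restriction on the key is tied to one subject, while the code is shared by the whole trial. With only two letters, knowing what one stands for gives the other. Anyone holding the key and the CRFs could then read the arm of every subject, including those still being treated or not yet enrolled. Under section 9, Data Collection, investigators keep copies of the completed CRFs.

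Closure is a clinical judgement at the site, so its credibility depends on the evaluator not knowing the arm. Debridement and choice of dressing are also left to the physician, so knowledge of the arm could affect handling as well as assessment. Self-reported VAS pain is exposed only indirectly, if what staff know reaches subjects. Tissue oxygenation, the primary endpoint, is measured by a device and is less exposed.

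**Working it through.** No figure in the plan bears on this point, so the check sets the sections side by side and then counts.

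**Step 1: what each section says about who is kept blind, and until when.**

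- Randomization and Blinding Procedure: staff directly involved, until the subject completes.
- Section 4, Randomization: involved Sponsor personnel, until the end of the study.
- Section 4, Interim Analysis: everyone except the Interim Analysis Committee, for closure data, until the final closure analysis.
- Description of Trial Design and General Statistical Considerations: double-blind, subject and evaluator blinded, with no end point given.

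Only the first is a rule on access to the key that reaches site staff, and it has the earliest end point. The second covers a different group. The third protects an endpoint and does not say who may hold the key. It still cannot be honoured if site staff have the key and the letters, because they could then tabulate closure by arm.

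**Step 2: when the first subject completes.** Under Study Visit 12/EOS, a subject whose wound "does not close completely by week 12 will exited from the study". Subjects whose wounds close go on to follow-up 3 months after closure. The first scheduled completion is therefore about 12 weeks after the first randomization, in a subject whose wound has not closed. Whether an early withdrawal counts as completing study activities is not stated.

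**Step 3: what one decoded letter reveals.** There are two codes. No section says that their meaning changes by subject, site or stratum. If it does not, one letter-arm pair determines the arm of all N subjects, so N − 1 others become readable.

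**Step 4: the count.**

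- If the sentence means all subjects: 0 exposed.
- If it is followed literally and A/B is fixed across the trial, the upper bound is N − 1. At the evaluable totals in section 4 this is 254 − 1 = 253, 508 − 1 = 507, or 2500 − 1 = 2499.

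These are numbers of subjects whose letter could be read. They are not subjects shown to be unblinded. Subjects finishing at about the same time as the first would already have been assessed, so nearly all is the fair description.

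**The case against.** The strongest reply is that the sentence limits access and grants it to nobody. It says who may hold the key and for how long, no section schedules a release, and the subject may simply stand for all subjects. The descriptions of the trial as double-blind and evaluator blinded show what the authors intended. This stands as far as intent goes. It does not supply the missing rule, because no section sets a later release point for site staff.

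Second, the section 4 bar names Sponsor personnel only, so different timing for site staff is not in itself a contradiction. That is right. The tension is with the blinding claims and with the blinding of closure.

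Third, one trial-wide meaning of A and B is assumed. That is also right: it is the natural reading but is not stated.

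Fourth, there are safeguards. The socks look identical, an independent statistical consultant supplies the list, and closure has explicit criteria (full re-epithelialization, no drainage, no need for a dressing) confirmed at two visits. These reduce the risk, but they do not restore an evaluator's blind once the letter is decoded.

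A reader might infer more than the text supports:

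- That the plan intends to unblind the sites as subjects finish. Nothing says so.
- That exposure can be counted from how fast subjects enrol. The documents give no accrual rate, and 254 is an evaluable number, with 5 to 15% attrition expected on top.
- That the key is opened at the 254-subject analysis. The sentence does not mention that analysis.

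**Conclusion.** The concern holds as a badly placed release point that conflicts with the rest of the plan, made worse by a two-letter code. It should be fixed, but it is not evidence that unblinding is planned. Exposure ranges from 0 subjects to potentially nearly all subjects other than the first to complete. The upper end needs three things: the sentence followed literally, the key actually passed to site staff at that point, and one meaning of A and B throughout. The size of any bias in closure cannot be derived from the documents.

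The coding weakness does not depend on how the sentence is read. With one meaning of A and B throughout, any single break of the code, for whatever reason, would reveal the whole allocation to anyone who can see the letters. The text available describes no procedure for unblinding a single subject.

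**What to change.** Replace the per-subject release point in Randomization and Blinding Procedure with one rule, reconciled with the Randomization and Interim Analysis parts of section 4. Under it, the key is withheld from all site staff, closure evaluators and sponsor staff involved in conduct until the database lock for the final closure analysis, and any earlier unblinding is limited to the single subject concerned. This costs one protocol paragraph, with no extra subjects, visits or assessments.

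As an optional and cheap improvement, use several codes per arm so that one break does not decode the trial. The cost is label printing and matching codes at resupply, since "Subjects will be supplied additional pairs as needed on a case by case basis". If stock is already labelled, the release rule can be corrected now and the extra codes can come with the next batch. Keep recording the dispensed code on the CRF, because the AT population in section 4 is analysed by the sock received.
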